1.5.3 Dose Selection Rationale

A variety of methods were utilized to determine the efficacious dose of VIS410 for the treatment of influenza in humans. These methods included evaluating doses and exposures to ascertain the VIS410 levels that satisfied such in vitro susceptibility measures as neutralization EC_{50} and binding affinity; utilizing mg/kg dose and PK data to bridge the efficacious dose from preclinical species to humans; and performing exploratory PK/PD analyses of serum and nasal exposure vs VIS410 antiviral activity in a human influenza virus challenge study.

VIS410 broadly neutralizes influenza A strains in vitro with EC_{50} values ranging from 0.03 to 64.2 $\mu\text{g/mL}$ (median of 3.15 $\mu\text{g/mL}$) and binds with high avidity (30 to 380 picomolar) to hemagglutinin across Group 1 and Group 2 subtypes. VIS410 doses of approximately 2300 mg, as used in the human challenge model, will result in C_{max} serum levels of ~ 873 $\mu\text{g/mL}$ for the duration of viral shedding (well above the median of EC_{50} value of 3.15 $\mu\text{g/mL}$). Furthermore, in preclinical animal studies, VIS410 demonstrated efficacy at doses of 20 to 30 mg/kg or less against various Group 1 and Group 2 influenza A strains with EC_{50} values ranging from 0.57 to 2.4 $\mu\text{g/mL}$. Using a standard mg/kg conversion, these doses equate to a 1500- to 2300-mg dose in humans (assuming a 75-kg subject).

In a human influenza virus challenge study, a single dose of 2300 mg demonstrated a significant reduction in viral AUC and peak viral load compared with placebo, suggesting that doses of approximately 2300 mg may be efficacious in naturally occurring influenza infection.

For strains with higher EC_{50} , doses greater than 2300 mg may be necessary to achieve adequate concentration at the primary site of infection. Based on these data, doses of 2000 and 4000 mg were selected for evaluation in this Phase 2b study. A dose of 4000 mg will ensure separation in VIS410 systemic exposures from the 2000-mg dose level to identify potential differences in safety and efficacy between the 2 doses. A dose level of 2000 mg provides a safety margin of approximately 9.4-fold to the nonclinical NOAEL (250 mg/kg), with the 4000-mg dose providing a safety margin of approximately 4.7-fold, assuming a 75-kg subject. In addition, in the Phase 1 study, doses of 2300 and 3800 mg were well tolerated following a pretreatment regimen of diphenhydramine plus ibuprofen or acetylsalicylic acid.

2.0 STUDY OBJECTIVES

2.1 Primary Objectives

2.1.1 Primary Efficacy Objective

- Evaluation of the effect of 2 dose levels of VIS410 + oseltamivir on clinical outcome as assessed by comparison of clinical status ordinal scale Day 7 scores between treatment groups, and between all VIS410 recipients versus placebo.

2.1.2 Primary Safety Objective

- Safety and tolerability of 2 dose levels of a single IV dose of VIS410 when administered in combination with oseltamivir in hospitalized subjects with influenza A infection

2.2 Secondary Objectives

- Among patients requiring supplemental oxygen therapy at the time of enrollment with baseline room air oxygen saturation of $\leq 92\%$, time to cessation of oxygen (O_2) support resulting in stable oxygen saturation (SpO_2) by pulse oximetry. Stable SpO_2 is defined as two consecutive SpO_2 values of $> 92\%$ on room air that are at least 8 hours apart.
- For any patient requiring supplemental oxygen therapy at the time of enrollment (regardless of oxygen saturation), time to cessation of oxygen support.
- Evaluate the effect of VIS410 + oseltamivir vs oseltamivir alone on the following endpoints:
 - Viral load in upper respiratory samples
 - Time to clinical response
 - Time to cessation of ventilator support
 - Time to resumption of normal activities
 - All-cause and attributable Day 14, 28, and 56 mortality
 - Clinical status ordinal scale mean area under the curve for Days 1-7 and Days 1-14 using linear numeric scores for the ordinal categories.
 - Comparison of clinical status ordinal scale scores for selected individual days (ie, Days 3, 4, 5, and 6)
 - Comparison of clinical status ordinal scale scores using modified ordinal scale criteria (ie, pooling of selected severity criteria scores)
 - Comparison of discrete ordinal scale parameters, including days of ventilator support, days in intensive care, and duration of hospitalization
 - Healthcare resource utilization
 - Analysis of time to alleviation of signs and symptoms of influenza in the subset of subjects able to complete the Influenza Patient Reported Outcomes (FluPRO) Questionnaire at baseline and post-dose by Kaplan Meier analysis
 - Proportion of subjects with new documented bacterial pneumonia/superinfection
 - Proportion of subjects with influenza-related complications
- Pharmacokinetics of VIS410 in serum
- Immunogenicity of VIS410

- Emergence of resistance to VIS410 and oseltamivir

2.3 Exploratory Objectives

- Evaluate the pharmacokinetics of VIS410 from nasopharyngeal secretions and tracheal aspirate (ventilated subjects only)
- Assess the effects of VIS410 on viral load in tracheal aspirate (ventilated subjects only)
- Assess correlations between virology, safety, VIS410 dose, pharmacokinetics, viral shedding, immunology, signs and symptoms of influenza, and other endpoints
- Assess the anti-influenza immune response

3.0 STUDY ENDPOINTS

3.1 Primary Endpoints

3.1.1 Primary Efficacy Endpoint

- The primary efficacy outcome analysis compares Day 7 clinical status ordinal scale scores between treatment groups, and between all VIS410 recipients versus placebo. Clinical status is measured daily for 14 days using the below seven-level ordinal scale, with the classifications presented from the worst clinical outcome to the best clinical outcome in descending order; for each day, subject status will be classified by the worst clinical outcome for which they qualify
 - Death
 - ICU stay with mechanical ventilation
 - ICU stay without mechanical ventilation
 - Non-ICU hospitalization with supplemental oxygen
 - Non-ICU hospitalization without supplemental oxygen
 - Discharge with partial resumption of normal activities
 - Discharge with full resumption of normal activities

3.1.2 Primary Safety Endpoint

- The proportion of subjects with AEs and SAEs following administration of VIS410.

3.2 Secondary Endpoints

- Among patients requiring supplemental oxygen therapy at the time of enrollment with baseline room air oxygen saturation of $\leq 92\%$, time to cessation of oxygen (O_2) support resulting in stable oxygen saturation (SpO_2) by pulse oximetry. Stable SpO_2 is defined as two consecutive SpO_2 values of $> 92\%$ on room air that are at least 8 hours apart.
- For any patient requiring supplemental oxygen therapy at the time of enrollment (regardless of oxygen saturation), time to cessation of oxygen support.
- The difference between VIS410 + oseltamivir and oseltamivir alone treatment groups in the following endpoints:
 - Peak viral load, viral AUC, duration of viral shedding, and time to resolution of viral load from nasopharyngeal swabs by $TCID_{50}$ and qRT-PCR
 - Time to clinical response defined as resolution of at least 4 of 5 vital signs
 - Afebrile with core temperature $\leq 37.8^\circ C$, without use of antipyretics (oral $\leq 37.2^\circ C$)
 - Oxygen saturation $\geq 95\%$ on room air without support or a return to pre-infection status, if pre-infection status was $< 95\%$
 - Pulse rate $\leq 100/min$
 - Systolic blood pressure ≥ 90 mm/Hg, without vasopressor use
 - Respiratory rate ≤ 24 beats per minute

- Clinical status ordinal scale mean area under curve for Days 1-7 and Days 1-14, using linear numeric scores for the ordinal categories.
- Comparison of clinical status ordinal scale scores for selected individual days (ie, Days 3, 4, 5, and 6)
- Comparison of clinical status ordinal scale scores using modified ordinal scale criteria (ie, pooling of selected severity criteria scores)
- Comparison of discrete ordinal scale parameters, including days of ventilator support, days in intensive care, and duration of hospitalization
- Number of days to resumption of usual activities
- All-cause and attributable mortality rates at Day 14, 28, and 56
- Total number of days in hospital and/or intensive care unit (ICU) from admission to discharge and rate of rehospitalization due to influenza A relapse/complication
- The incidence, severity, and duration of signs and symptoms of influenza-like illness as assessed by the FluPRO Questionnaire (see Appendix 14.1)
- Analysis of time to alleviation of signs and symptoms of influenza in the subset of subjects able to complete the Influenza Patient Reported Outcomes (FluPRO) Questionnaire at baseline and post-dose by Kaplan Meier analysis
- The percentage of subjects with new bacterial pneumonia/superinfection
- The percentage of subjects with influenza-related complications
- VIS410 population pharmacokinetic (PK) parameters in serum
- Titer of anti-VIS410 antibody positive samples
- Genotypic and/or phenotypic assessment to determine the emergence of VIS410 and oseltamivir-resistant viruses

3.3 Exploratory Endpoints

- Population PK parameters of VIS410 from nasopharyngeal secretions
- VIS410 concentrations in tracheal aspirates
- The difference in viral load between VIS410 + oseltamivir and oseltamivir alone treatment groups in tracheal aspirates of subjects on mechanical ventilation
- Titer of anti-influenza A antibodies by hemagglutinin inhibition assay (HAI) in serum
- Correlations between serum and/or nasopharyngeal PK with viral load, clinical symptoms, presence of ADAs, safety, and additional endpoints

4.0 STUDY DESIGN

4.1 Overview

This is a Phase 2b multicenter, randomized, double-blind, controlled study comparing the efficacy and safety of 2 dose levels of VIS410 (2000 and 4000 mg) in combination with oseltamivir vs oseltamivir alone in hospitalized subjects with influenza A infection requiring oxygen. Subjects will be randomly assigned at a ratio of 1:1:1 using a permuted block randomization method to receive VIS410 at a dose of 2000 mg (low dose) or 4000 mg (high dose) or placebo (0.9% sodium chloride), administered as a single IV infusion over 2 hours.

Randomization will be stratified by presence or absence of positive pressure ventilation (PPV) at baseline to ensure an even distribution across treatment arms (see Section 10.2). All subjects will receive oseltamivir 75 mg twice daily (BID) for 5 days (total of 10 doses) as part of standard of care (SOC). All subjects will also receive a pretreatment regimen of diphenhydramine 50 mg PO or IV plus either ibuprofen 400 mg PO or acetylsalicylic acid 320-325 mg PO 60 minutes before VIS410/placebo infusion. Approximately 120 evaluable subjects (40/arm) with confirmed influenza A infection will be treated.

Subjects admitted to the hospital within 5 days of onset of initial symptoms who require supplemental oxygen will undergo a rapid influenza test (supplied by the Sponsor) or a PCR, fluorescent immunoassay (FIA), or enzyme-linked immunosorbent assay (ELISA) test to confirm influenza A infection. Subjects diagnosed with influenza A will undergo the screening procedures to confirm eligibility. Study assessments are outlined in Table 1, Schedule of Assessments.

Eligible subjects will be randomized to receive either oseltamivir + VIS410 2000 mg, oseltamivir + VIS410 4000 mg, or oseltamivir + placebo (0.9% sodium chloride) at a ratio of 1:1:1 using a permuted block randomization method summarized in Table 6.

Table 6. Permuted Block Randomization Method

Subjects	Treatment	VIS410 Dose ^a	Oseltamivir Dose ^b	Infusion
n = 40	VIS410 + oseltamivir	2000 mg IV	75 mg administered BID for a minimum of 5 days	Infused over 120 minutes
n = 40	VIS410 + oseltamivir	4000 mg IV		
n = 40	Placebo ^c + oseltamivir	0 mg IV		

^a Dose administered in 200 mL.

^b Dosage and administration should follow local prescribing information for oseltamivir based on renal function.

^c 0.9% sodium chloride (200 mL).

Oseltamivir (Tamiflu) will be provided by the Sponsor. Treatment with oseltamivir may be extended for up to 5 additional days (up to 20 doses of total therapy) if clinical symptoms

warrant further treatment as assessed by the Investigator. Note: based on SOC, subjects may have started oseltamivir therapy prior to randomization.

Study assessments are outlined in Table 1. Subjects discharged from the hospital prior to Day 14 will attend the applicable outpatient follow-up visit(s) (eg, Day 3, Day 5, Day 7, Day 14) per Table 1.

4.2 Study Duration

The total study duration for each subject (screening through study exit) will be approximately 8 weeks (Day 56).

4.3 Data Safety Monitoring Board

An independent data safety monitoring board (DSMB) will be established to review all available safety data after 30 subjects, and subsequently, approximately 70 subjects, have completed study Day 14. The assessment of safety will be determined from vital sign measurements, physical examinations, hematology, chemistry and urinalysis laboratory testing, 12-lead electrocardiograms (ECGs), use of concomitant medications, and review of AEs. Based on the safety data provided, the DSMB will determine if it is acceptable to continue the study or reduce the dose as appropriate.

Additional DSMB reviews can occur throughout the trial as deemed necessary by the DSMB or Sponsor to ensure subject safety and well-being. Study enrollment and dosing will continue while the DSMB evaluates data.

Further details will be described in a separate DSMB charter.

4.4 Discussion of Study Design

This study is a Phase 2b, multicenter, randomized, double-blind study of 2 doses of VIS410 vs placebo in the treatment of hospitalized subjects with influenza A infection requiring oxygen support. VIS410 and placebo will be administered on top of the SOC, ie, oseltamivir.

The dose of oseltamivir (75 mg BID for 5 days) was chosen for this study based on the approved dose in the United States and other regions for the treatment of uncomplicated influenza infection. The dosage regimen of oseltamivir as the SOC in this study serves as a clinically appropriate, ethically acceptable treatment.

The study will be blinded using placebo infusion (as described in Section 7.2) to prevent bias in the assessment of effect. The investigative site personnel, the Sponsor and their representatives involved in the monitoring or conducting the study, and the subjects will all be blinded to the study drug codes.

5.0 STUDY POPULATION

5.1 Number of Subjects

Approximately 120 evaluable subjects will be randomized into 3 treatment arms: VIS410 2000mg, VIS410 4000 mg, and placebo.

5.2 Selection of Study Population

The study population comprises subjects at least 18 years of age with confirmed influenza A infection who satisfy all inclusion and exclusion criteria, and who do not have any conditions, in the opinion of the Investigator, that may place the subject(s) at increased risk, confound study data, or significantly interfere with study participation. Section 5.2.1 and Section 5.2.2, which describe the inclusion and exclusion criteria, respectively.

5.2.1 Inclusion Criteria

Subjects meeting all of the following criteria are eligible to participate in this study:

1. Male and female subjects aged ≥ 18 years. For a country where the legal age of consent is >18 years old, the country requirements should be followed.
2. Test positive for influenza A by rapid antigen test or with another commercially available test on an adequate nasopharyngeal specimen in accordance with the manufacturer's instructions, or an acceptable local test including, PCR, FIA, or ELISA.
3. Onset of influenza symptoms no more than 5 days before VIS410/placebo infusion; symptoms may include cough, dyspnea, sore throat, fever, myalgias, headache, nasal symptoms (rhinorrhea, congestion), fatigue, diarrhea, anorexia, nausea, and vomiting.
4. Requirement for oxygen support including any positive pressure ventilation (PPV).
5. Women of childbearing potential must have a negative pregnancy test within 2 days prior to VIS410/placebo infusion.
6. Women should fulfill one of the following criteria:
 - a. Post-menopausal: either amenorrhea ≥ 12 months or follicle stimulating hormone > 40 mIU/mL as documented in their medical history
 - b. Surgically sterile; hysterectomy, bilateral oophorectomy, or tubal ligation
 - c. Women of childbearing potential participating in heterosexual relations must be willing to use adequate contraception from screening until 60 days post-VIS410/placebo infusion (see Section 6.2).
7. Non-vasectomized (or vasectomized less than 6 months prior to dosing) male subjects who have a female partner of childbearing potential must use an effective birth control method (see Section 6.2) when having heterosexual intercourse, from screening until 60 days post-VIS410/placebo infusion.
8. Subject is able and willing to comply with study procedures, as per protocol.
9. Subject, or a legally acceptable representative, is able to understand the purpose and risks of the study and willing to give voluntary written informed consent.

5.2.2 Exclusion Criteria

Subjects meeting any of the following criteria are excluded from participation in this study:

1. Known or suspected intolerance or hypersensitivity to VIS410, oseltamivir, pretreatment medications (diphenhydramine, or to both ibuprofen and acetylsalicylic acid [ASA]), or closely related compounds (eg, other monoclonal antibodies).
2. Subjects who have received VIS410 in the past.
3. Subjects who have a history of receiving monoclonal antibody products within 3 months prior to VIS410/placebo dosing or planned administration of another monoclonal antibody during the study period.
4. Subjects who have taken more than 6 doses of an approved antiviral therapy for influenza within the prior 96 hours (eg, oral oseltamivir, inhaled zanamivir, IV peramivir, or oral ribavirin) between onset of symptoms and VIS410/placebo dosing.
5. Subjects with known co-infection with influenza B or other viral respiratory infections (eg, RSV, parainfluenza viruses, respiratory adenoviruses).
6. Subjects with lung transplant or history of severe chronic lung disease, including cystic fibrosis or any condition requiring home oxygen therapy.
7. Subjects on extracorporeal membrane oxygenation at time of randomization.
8. Subjects with ESRD who are not undergoing hemodialysis.
9. Subjects with active graft-vs-host disease, hematopoietic stem cell transplant within the previous 90 days, or human immunodeficiency virus infection with a CD4 cell count of less than 200 per cubic millimeter.
10. High probability of mortality within 48 hours of randomization as determined by the Investigator.
11. Women who are pregnant, breast-feeding, or considering to become pregnant.
12. Subjects in whom nasopharyngeal swabbing is not possible.
13. Subjects weighing less than 45 kg.
14. Enrollment in any other investigational drug or device study, any disease or vaccine study within 30 days prior to Day 1 or within 5 half-lives of the investigational compound, whichever is longer.
15. Presence of any preexisting illness that, in the opinion of the Investigator, would place the subject at an unreasonably increased risk through participation in this study.
16. Subjects unable to comply with study protocol procedures and study visit schedules for whatever reason.
17. Known or suspected alcohol or drug abuse, that is, abuse of a level that would compromise the safety or cooperation of the subject in the opinion of the Investigator.

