Ibuprofen and acetylsalicylic acid are contraindicated in patients with known hypersensitivity to NSAIDs and acetylsalicylic acid-induced asthma. Ibuprofen is contraindicated for treatment of perioperative pain in the setting of coronary artery bypass graft surgery.

Ibuprofen may cause an increased risk of serious cardiovascular thrombotic events, myocardial infarction, and stroke, which can be fatal. Patients with cardiovascular disease or risk factors for cardiovascular disease may be at greater risk.

NSAIDs cause an increased risk of serious GI AEs, including bleeding, ulceration, and perforation of the stomach or intestines, which can be fatal. Elderly patients are at greater risk for serious GI events.

Long-term administration of NSAIDs has resulted in renal injury. Patients at greatest risk of this reaction are those with impaired renal function, heart failure, liver dysfunction, those taking diuretics and ACE inhibitors, and the elderly. NSAIDs should be avoided in patients with severe renal failure.

NSAIDs can cause serious skin AEs, such as exfoliative dermatitis, Stevens-Johnson syndrome, and toxic epidermal necrolysis.

Acetylsalicylic acid can result in GI side effects, such as stomach pain, heartburn, nausea, vomiting, dyspepsia, and GI bleed. Patients with history of active peptic ulcer disease should avoid acetylsalicylic acid.

The following adverse reactions have been reported following acetylsalicylic acid administration:

- Body as a whole: Fever, hypothermia, thirst
- Cardiovascular: Dysrhythmias, hypotension, tachycardia
- Central nervous system: Agitation, cerebral edema, coma, confusion, dizziness, headache, subdural or intracranial hemorrhage, lethargy, seizures
- Fluid and electrolyte: Dehydration, hyperkalemia, metabolic acidosis, respiratory alkalosis
- Gastrointestinal: Dyspepsia, GI bleeding, ulceration and perforation, nausea, vomiting, transient elevations of hepatic enzymes, hepatitis, Reye syndrome, pancreatitis
- Hematologic: Prolongation of the prothrombin time, disseminated intravascular coagulation, coagulopathy, thrombocytopenia
- Hypersensitivity: Acute anaphylaxis, angioedema, asthma, bronchospasm, laryngeal edema, urticaria
- Musculoskeletal: Rhabdomyolysis
- Metabolism: Hypoglycemia (in children), hyperglycemia
- Reproductive: Prolonged pregnancy and labor, stillbirths, lower birth weight infants, antepartum and postpartum bleeding
- Respiratory: Hyperpnea, pulmonary edema, tachypnea

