7.5 Pretreatment Regimen

All subjects will be given a pretreatment regimen of PO or IV diphenhydramine 50 mg plus either ibuprofen 400 mg or acetylsalicylic acid 320-325 mg PO or crushed and given through the nasogastric tube approximately 60 minutes before IV infusion of VIS410/placebo.

If the subject has any history of delayed gastric emptying, including premenstruation syndrome or menstruation, the subject may receive premedications 120 minutes prior to IV infusion of VIS410/placebo.

Refer to the Pharmacy Manual for directions on storage, handling, stability data, and preparation and use of diphenhydramine, ibuprofen, and acetylsalicylic acid.

For more information, refer to the prescribing information for ibuprofen¹⁰ and acetylsalicylic acid.¹¹

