8.3.2 Day of Treatment Procedures (Day 1)

On Day 1, eligibility of the subjects will be confirmed and assessments will be performed as described in Table 1.

All results from the screening procedures required to evaluate eligibility must be available prior to randomization on Day 1. Any abnormal assessment at the screening will be assessed according to its clinical relevance, and if found relevant, the subject will not be included in the study.

Once a subject has fulfilled the entry criteria, he/she will be assigned a unique identifier. The site's unblinded pharmacist or properly trained designee will randomize the subject using the IWRS.

On Day 1, all subjects will receive the pretreatment regimen prior to receiving VIS410/placebo.

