9.1.3 Adverse Event of Special Interest

An adverse event of special interest (AESI; serious or non-serious) is one of scientific and medical concern specific to the Sponsor's product or program, for which ongoing monitoring by the Sponsor may be warranted. Such an event should be entered into EDC in a timely manner and if applicable, reported as an SAE. Depending on the nature of the event, rapid communication by the trial Sponsor to other parties (eg, regulators) might also be warranted (based on CIOMS VI).

For VIS410, the AESIs include the following:

- Abdominal cramping
- Diarrhea/Loose stool
- Nausea
- Vomiting
- Pruritus
- Rash
- Hypotension
- Throat tightening
- Trouble breathing or wheezing

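### Exclusion 1 lets through subjects for whom Protocol Section 1.5.1.3 calls both ibuprofen and aspirin contraindicated, while Sections 7.5 and 8.3.2 require one of the two in every subject

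*Protocol*

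**What the plan says.** Three parts of the protocol bear on this.

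- **Eligibility.** Exclusion 1 in Section 5.2.2, worded identically in the synopsis, covers known or suspected intolerance or hypersensitivity to the study drugs and to "pretreatment medications (diphenhydramine, or to both ibuprofen and acetylsalicylic acid [ASA"]). For the NSAID component, the problem must extend to both drugs before it excludes.
- **Risk statement.** Section 1.5.1.3 says: "Ibuprofen and acetylsalicylic acid are contraindicated in patients with known hypersensitivity to NSAIDs and acetylsalicylic acid-induced asthma". It treats the two drugs together and does not offer one as a substitute for the other.
- **Treatment requirement.** Section 7.5: "All subjects will be given a pretreatment regimen of PO or IV diphenhydramine 50 mg plus either ibuprofen 400 mg or acetylsalicylic acid". Section 8.3.2: "On Day 1, all subjects will receive the pretreatment regimen prior to receiving VIS410/placebo". The synopsis and Sections 4.1 and 10.2 repeat the requirement. No NSAID-free option or exemption is described.

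The requirement is deliberate. Section 1.3.3.1 concludes that adding an NSAID to the antihistamine was needed to reduce the gastrointestinal events further. SAP Section 8 tabulates how many subjects received the NSAID as the protocol directs, and treats non-receipt as a dosing departure to be summarised.

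**The concern.** Exclusion 1 works on the premise that a subject who cannot take one of the two drugs can take the other. Section 1.5.1.3 does not share that premise. A subject can therefore pass the only criterion that mentions these drugs, fall under a contraindication the protocol itself states, and still be directed to take one of them.

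The main stake is the subject's safety. Everyone enrolled needs oxygen support (Inclusion 4). Asthma as such is not excluded: Exclusion 6 removes lung transplant, severe chronic lung disease and home-oxygen conditions only. Underlying lung disease is a planned subgroup (Protocol Section 10.6.2, SAP Section 4.3), so such patients are expected.

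A lesser stake is how events are read. Section 1.5.1.3 lists anaphylaxis, bronchospasm, laryngeal edema and urticaria among reported aspirin reactions. The events of special interest for VIS410 in Section 9.1.3 overlap with these and include "Trouble breathing or wheezing".

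**Working it through.** The plan gives no figure to reproduce. The check is whether Exclusion 1, Section 1.5.1.3 and Sections 7.5/8.3.2 can all be followed for the same subject. Four kinds of subject separate the cases.

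1. *Recognised hypersensitivity to NSAIDs as a class.* This would normally count as hypersensitivity to both drugs, so Exclusion 1 applies. No conflict.
2. *ASA-induced asthma, no known ibuprofen reaction.* On its face Exclusion 1 is not met. Section 1.5.1.3 contraindicates both drugs. Sections 7.5 and 8.3.2 require one of them. The three texts cannot all be followed.
3. *Known hypersensitivity to one NSAID only.* Exclusion 1 is not met, and one of the drugs is required. Whether Section 1.5.1.3 applies depends on whether its phrase about hypersensitivity to NSAIDs includes a reaction to a single agent. The conflict is arguable.
4. *Simple intolerance of one drug, without hypersensitivity.* Exclusion 1 is not met, Section 1.5.1.3 is not engaged, and the subject takes the other drug. No conflict.

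The gap is therefore case 2, and arguably case 3.

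Next, whether anything else keeps these subjects out. Exclusion 15 concerns "Presence of any preexisting illness that, in the opinion of the Investigator, would place the subject at an unreasonably increased risk". Section 5.2 describes the population as subjects "who do not have any conditions, in the opinion of the Investigator, that may place the subject(s) at increased risk". Both rest on the investigator's opinion and name neither condition. Inclusion 8 and Exclusion 16 concern ability to comply with protocol procedures, and again do not mention it. The extension of Exclusion 1 to related compounds gives monoclonal antibodies as its only example.

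Timing of a possible reaction: premedication is given about 60 minutes before a 2-hour infusion (Sections 7.5 and 7.3). A reaction beginning more than about 60 minutes after the premedication would start once the infusion is under way. Under SAP Section 12.1, an event on the infusion day is treatment-emergent only if recorded as beginning after the infusion.

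Size: the documents give no prevalence. Assume, for illustration only, that 1% to 3% of subjects have ASA-induced asthma or a past reaction to one NSAID:

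- 0.01 × 120 = 1.2 subjects; 0.03 × 120 = 3.6 subjects.
- Spread over three equal arms: 1.2 / 3 = 0.4 to 3.6 / 3 = 1.2 per arm.

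Section 11.4 pauses dosing at 4 treatment-related serious adverse events. Even at 3.6 subjects, with every one having a serious reaction judged related, one event each would fall short of 4. Such events could add to a count reached for other reasons.

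**The case against.** The best reply is that a site need not enrol this subject. Someone for whom both drugs are contraindicated cannot complete a mandatory procedure and can reasonably be said to fail Inclusion 8 and meet Exclusion 16. Exclusion 1 covers suspected as well as known hypersensitivity, and its monoclonal-antibody wording is an example, not a limit. An investigator who has read Section 1.5.1.3 could suspect hypersensitivity to both drugs in ASA-induced asthma. Section 5.2 sets a lower threshold than Exclusion 15, and Section 7.5 points to the prescribing information.

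This stands as far as it goes: the site has routes to exclude, and it would be wrong to infer that enrolment is unavoidable. But these routes permit exclusion without clearly requiring it. The one criterion that addresses these drugs signals that a reaction to one of them is acceptable, and a specific rule tends to be followed over a general one.

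It is also fair to object that Section 1.5.1.3 makes a class statement. It does not say that every intolerance of one agent rules out the other, so the wording of Exclusion 1 is coherent for case 4 above. That narrows the point, as set out in the working.

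Finally, the consequences for safety inference are limited. Placebo subjects receive the same premedication, treatment is blinded, and anaphylaxis and hypersensitivity are determined by clinical evaluation before database lock (SAP Section 12.1), not by automatic counting. This stands.

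**Conclusion.** The inconsistency is real and lies in the current text. As written, the protocol can require a drug it calls contraindicated, in a subject who already needs oxygen. It is clear for ASA-induced asthma without a known ibuprofen reaction, and arguable for hypersensitivity to a single NSAID. The number affected is unknown and probably small; the range of 1.2 to 3.6 subjects rests entirely on an assumed prevalence, pools the clear and arguable cases, and ignores subjects whom sites would exclude under the general clauses.

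Two stronger readings are tempting and not supported. First, a reader might infer that the VIS410 safety comparison is biased. Premedication is the same in all arms, so such reactions are not expected to differ systematically between them; only chance imbalance of about one subject per arm is in question under the assumption above. Second, a reader might infer that every premedication reaction would enter the VIS410 safety results. Same-day events starting before the infusion are not treatment-emergent under the SAP, and the primary safety endpoint counts events following administration. What remains is that a reaction starting after the infusion begins could be recorded as a VIS410 event of special interest or, if serious and judged related, count toward the four-event pause.

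The primary efficacy analysis is not affected.

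**What to change.** Reconcile Exclusion 1 (synopsis and Section 5.2.2), the contraindication statement in Section 1.5.1.3 and the premedication requirement in Sections 7.5 and 8.3.2. The test is that no subject who meets a contraindication stated in Section 1.5.1.3 can pass eligibility and still be required to take one of the two drugs. Whether the exclusion, the requirement or the risk statement changes is for the sponsor's clinical team; this review proposes no clinical rule. Put the reconciled wording into the eligibility check completed before randomisation, so that it does not depend on a site connecting separate sections. If the premedication requirement changes, its repetitions in the synopsis and Sections 4.1 and 10.2, and the compliance summary in SAP Section 8, should follow.

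The cost is about one sentence in each affected place, by amendment. The downside is that a few otherwise eligible subjects may be excluded or handled differently.
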